Research Protocol (revised July 7, 2014)

Project Title: Mammographic Density and Soy Isoflavones

Principal Investigator: [name].

Dept of Preventive Medicine and Community Health
University of Texas Medical Branch, [name]
[contact]
[contact]
[contact]

Abstract. Populations consuming high levels of soy, as in many Asian countries, have lower levels of ovarian hormones, lower rates of breast cancer, and reduced mammographic density than populations consuming typical Western diets. These observations may in part be explained by our clinical studies that found ovarian hormone levels of premenopausal women to be lowest while they were consuming a diet that provided 15% energy from soymilk containing weakly estrogenic isoflavones. No adverse effects were observed. Further questions are whether isoflavones are the critical components influencing breast cancer risk and whether they do so by affecting other reversible risk markers for breast cancer, such as breast density. Women with dense breasts have a 4-6 fold excess risk of developing breast cancer. Moreover, greater breast density makes it more difficult to detect early breast cancer by mammography. To test the hypothesis that consumption of soy isoflavones reduces breast density, we propose a randomized, double-blind study, with two arms, and 100 premenopausal women in each arm. Women will be recruited and randomly allocated to take soy isoflavone pills (treatment) or placebo pills containing no isoflavones (control) for 2 years. The daily dose will be 120 mg of total isoflavones. Both treatment and placebo pills will contain multi-vitamin and minerals. Women will provide blood and urine samples before and during the supplement intervention period for the analyses of ovarian hormones and isoflavones. At baseline and after the intervention period, subjects will be examined for breast density by mammography and magnetic resonance imaging. The efficacy of the intervention will be determined by comparing mean changes of dense breast tissue over the 2-year intervention period in the two groups with adjustment for baseline values and individual patient characteristics of interest. We hypothesize that 1 to 2 years of a soy isoflavone supplement in premenopausal women will reduce the effects of endogenous estrogens and reduce progesterone levels further, which will explain a corresponding decrease in breast density. Our research results will have significant implications for breast cancer risk reduction. Reducing breast density can be expected to reduce the volume of target tissue at risk for breast cancer development and will improve the sensitivity of mammography for screening. The study may lead to a novel, non-invasive and economical approach to breast cancer prevention.

Introduction: In two separate soy feeding studies, we have successfully lowered not only levels of estrogens (by 25-40%) but also progesterone (by 40%) in all 16 premenopausal women after only 1 month of soy feeding (1-5). In these prior studies, only 400 kilocalories of the daily energy intakes (~15%) of each subject was replaced by soymilk and the isoflavone intakes were 100-200 mg (as aglycones) per day. Soy feeding also lowered estrone sulfate by 15% and androstenedione by 20% in 12 postmenopausal women after 4 months. In premenopausal woman, soymilk with or without isoflavones

was highly effective in lowering estrogens and progesterone. However, a soy diet with higher level of isoflavones decreased progesterone levels further compared to a soy diet without isoflavones. The isoflavone-rich soy diet also increased urinary excretion of the “anticarcinogenic” 2-hydroxyestrone without affecting the excretion of the “carcinogenic” 16 α -hydroxyestrone. Results from statistical models suggest that the amount and the source of protein and isoflavones are main factors that modify ovarian hormone levels. In this proposal, we will determine the roles of isoflavones on breast cancer risk reduction by analyzing their influences on breast and bone density. No adverse reproductive effects (e.g. amenorrhea in premenopausal women or thickened endometrium and increased vaginal cornification in postmenopausal women) have been observed in our studies. The magnitude of changes in the ovarian steroids in our study was similar to the differences of these steroids found in populations with widely different risks for breast cancer. Our results may explain why Asian women consuming soy have a lower risk for breast cancer than women consuming western diets. Our results, therefore, have physiologic significance and implications for breast cancer prevention.

Objective: Further important questions are whether isoflavones are the active component(s) and whether isoflavones can favorably influence other known and preventable risk factors, such as breast density. Breast tissue consists of radiologically dense fibroglandular tissue and radiologically translucent adipose tissue. Breast cancer originates in fibroglandular tissue. Women with higher breast density have a 4-6 fold higher risk of developing breast cancer; moreover, greater breast density makes it harder to detect early breast cancer by mammography (“masking effect”). However, unlike many other reproductive risk factors for breast cancer, such as ages of menarche, menopause and first full term pregnancy, increased breast density is a risk factor that can be reversed. Breast density is, therefore, a potential measure of efficacy for preventive interventions. Moreover, breast density may reflect cumulative past exposure to endogenous ovarian steroids and, thus, be a better intermediate surrogate marker for breast cancer risk than, for example, short term monitoring of serum levels of ovarian steroids. We propose to test the hypothesis that continuous consumption of isoflavones beyond 1 month will reduce ovarian steroid hormones and lead to a corresponding reduction in breast density. Isoflavones bind to estrogen receptors with affinity and specificity differing from 17 β -estradiol. Because bone is also an estrogen responsive tissue, the effect of isoflavones on bone metabolism in premenopausal women cannot be easily predicted and should, therefore, be monitored and studied as proposed here.

Hypothesis/Aims: Isoflavones lower progesterone levels but have no immediate effects on circulating 17 β -estradiol. [Note: there could be a delay effect on 17 β -estradiol due to feedback regulation.] Because isoflavones bind to estrogen receptors (ERs), they can displace estrogens from ERs, thereby blocking the effects of endogenously formed estrogens on breast tissue without immediately affecting circulating levels of estrogens. If this occurs, the markers for studying such effects are breast density or bone density. The hypotheses to be tested are that chronic soy isoflavone consumption will decrease progesterone further and soy isoflavones will compete with 17 β -estradiol for binding to ERs, thereby diminishing the effect of estradiol on breast (and bone) tissue, leading to a corresponding decrease in breast density (and possibly bone density). We will determine:

Aim #1: effects of continuing exposure to soy isoflavone beyond 1 month on the time-dependence of the levels of ovarian steroid and other hormones

Aim #2: effects of chronic soy isoflavone ingestion on breast and bone density

Aim #3: the interactions of isoflavones and other nutrients on breast density using statistical models

Aim #4: the safety of chronic soy isoflavone ingestion

Experimental Design and Methods: These aims will be achieved by a prospective, parallel 2-arm, repeated measures, randomized, double blind, placebo controlled study. After a successful completion of a 2-month baseline observation, qualified women will be randomly allocated to either placebo pills (control) or 120 mg isoflavone pills (aglycones, treatment) 5 days per week for 2 years with blinding of subjects, research staff and investigators to the supplement assignments. Both treatment and placebo pills will contain required daily intake of multi-vitamin and minerals. The main outcomes are: 1) breast density by mammography and MRI, 2) bone density by dual energy x-ray absorptiometry (DEXA) and 3) serum, nipple aspirate, and urinary levels of estrogens, progesterone, and other breast cancer risk markers, and changes from baseline to intervention. The explanatory variables are nutrient intakes, isoflavone intakes, urinary and plasma levels of isoflavones, demographic data (body weight, height), and reproductive history. Breast (and bone) density is chosen as a major outcome of interest because it is an index of cumulative exposure to ovarian hormones and is postulated to be intermediate biomarkers for breast cancer risk (6). To monitor safety, blood chemistries including liver and thyroid function tests, lipid profiles, blood cell counts, menstrual cycle lengths, and cytology of nipple fluid aspirates (to determine presence or absence of hyperplastic epithelial cells), endometrial histology, vaginal smear cytology, unexpected vaginal bleeding, breast lumps, and bone density will be monitored once every three months during all outpatient visits.

Inclusion/exclusion criteria: Women must be 30-40 years of age with regular cycles, FSH levels \leq 10 mU/ml and mid-luteal phase progesterone $>$ 8 ng/ml. Mammograms must be normal. Exclusions include use of contraceptive agents, other exogenous hormones, medications known to affect mammographic density, any medically prescribed diet, current pregnancy or lactation, previous history of cancer, breast cancer in a first degree relative, breast augmentation, reduction, or lifting, and per- or postmenopausal status.

All procedures (mammography, MRI) and samples (fasting blood, overnight 12-hr urine, and nipple fluid) will be obtained during the mid-luteal phase of the menstrual cycle (between cycle days 20 to 24 preferably day 22) when progesterone levels peak. Subjects will record cycle day 1 (onset of menstrual spotting) throughout the study and complete a dietary habit history questionnaire (DAQ) (8) and reproductive history and general health history questionnaires (PHQF).

During each GCRC outpatient visit, subjects will bring a 12-hr overnight urine (stored in a urine jug containing sodium azide and glycerol), 24-hour food records. Menstrual cycle lengths and body weights will be recorded and fasting blood samples obtained for serum chemistries, liver and thyroid functions, lipid profiles, and steroid hormones. Breast fluid secretors will provide nipple fluid aspirates for analysis of epithelial cytology and hormones.

Baseline observations (2 menstrual cycles): There will be 3 GCRC visits per menstrual cycle for at least 2 cycles. Complete history, physical examination and a Pap smears will be obtained. Subjects who qualify will then be randomized, undergo mammography (a standard screening mammography and one extra view), bilateral breast MRI, and a bone density measurement by DEXA (L2 to L4 and hip).

Pill supplementation intervention period (24 months): Isoflavone or control pill supplements will begin on the second day of menstrual bleeding soon after the baseline observation period. Every three months (~ seasonally) subjects will visit the GCRC on day 22 of a cycle. At these visits, subjects will be provided with the assigned supplement pre-packaged for daily dose and consumption. Subjects will be randomly assigned to placebo or treatment in blocks of six to assure equal sizes of the pill group and of the sub-groups for blood sampling, using the PLAN procedure in SAS® (9).

If more than 6% of subjects (12 subjects) develop amenorrhea, we will break the code for these women. A transvaginal probe ultrasonography and an endometrial biopsy will be performed if amenorrhea occurs. If amenorrhea is related to soy isoflavone treatment, the study will be terminated. If this occurs, a statistically significant change in breast density is then expected because the progesterone levels of these women will be <1 ng/ml. The mammography, MRI and bone density measurements will be performed at yearly intervals and whenever subjects notify us of their intent to leave the study.

Statistical Analysis. The primary outcome variables are measures of breast density (mammographic density and relative volumes of parenchymal and adipose tissues by MRI). The main analysis will assess changes in breast density (BD) parameters over the 2-year follow-up period, measured at baseline, at one year and at two years. The efficacy analysis for the measures of BD will be analyzed primarily through mixed models for continuous outcome measures. This class of linear models can accommodate missing data and allows inclusion of time-dependent covariates for outcomes that are approximately normally distributed. Software is widely available (e.g., MIXED procedure in SAS®). We will model the marginal responses of the breast density parameters for each intervention group. The main effects of time, supplement group, and the (time x supplement group) interaction will be assessed. Time-dependent covariates (e.g., BMI) and time-independent variables (e.g., parity, age of menarche, race/ethnicity), including potential confounding variables, can be added to the models. The analysis will proceed with an intent-to-treat principle in which any subject randomized to a treatment group (i.e., placebo or soy isoflavones) with at least one post-baseline BD measure will be included in the statistical analyses. Some analyses will be conducted which will include only those patients with complete data up to a designated data collection time point (e.g., 12 months, 24 months, etc).

Power analysis and sample size justification. The main assessment of outcome is the change from baseline in percent dense tissue. The hypothesized mean change in area of dense tissue in the soy isoflavone group will be a decrease between 10 and 15 percentage points on average, while the placebo group will remain about the same (6; 10-15). Using a two group t-test with a 0.05 two-sided significance level, and estimates of the SDs that range from 20 to 10, we will have 80% power to detect changes in mean percent of dense tissue of -10% to -20%. If we experience a 20 to 30% dropout rate, the study can still detect changes of -10% if $SD \leq 20$, and -15% or larger for $SD \leq 25$. Our choice of 100 patients per arm is robust to any violations of our assumptions, for example unanticipated study variation or higher dropout rates than expected. Additionally, we can expect the study to have even greater power than we estimate since the proposed analyses (ANCOVA, mixed models) exhibit greater power characteristics than the t-tests upon which our power analysis is based. With an estimated attrition rate of 15% over the length of the study, 100 subjects per arm should provide 85 evaluable subjects at the completion of the study. We will recruit until 200 women complete at least 1.5 years of supplement.

Results expected. Increasing the duration of consumption of soy isoflavones is expected to decrease circulating (and nipple fluid) ovarian steroids, mammographic

density, and volume of breast with parenchymal tissue relative to adipose tissue. We expect the rates of these decreases to be greater in the isoflavone group than in the placebo group. Proliferation markers in nipple aspirates and the presence of hyperplastic epithelial cells in nipple aspirates may indicate the degree of stimulatory effects of isoflavones on breast tissues. This study will show whether breast MRI which measures 3-D features of the breasts may be more sensitive in detecting breast density changes than mammography, which is a 2-D assessment. Ability to use MRI (no radiation exposure) to measure breast density will allow us to assess in the future whether soy pill supplementation intervention on breast density and breast cancer prevention may be more effective if initiated during puberty than during adulthood, as data from animal studies have shown. The effect of isoflavones on bone is hard to predict and will be examined in this study.

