Lowering of female hormones due to prolonged soy isoflavone ingestion may lower bone density, which could increase the risk of eventually developing osteoporosis (thin bones) and bone fractures. But this is not a known risk. Soy isoflavones have been shown to improve bone mineral density in animals. Asian populations consuming high levels of soy have lower rates of hip fracture compared to western countries. Because the current available information does not allow us to estimate the benefit and the risk of soy consumption on bone density, observations about bone is a part of this study. The risk of osteoporosis might also be increased if subject's calcium intake is not sufficient during the study. Subjects will be advised to adjust their calcium intake if needed to maintain an adequate intake.

Potential adverse effects such as lengthening of the menstrual cycle and nipple fluid cytology will be looked for closely during this study. If menstrual cycle lengths increase by more than 2 weeks in 12% of the participants (e.g. 12 subjects) for more than 3 cycles, the pill assignment codes for these women will be examined to assess if this is intervention-related. If this is associated with treatment, the ovarian hormones of these subjects will be immediately analyzed. The luteal progesterone levels in these women should be less than 1 ng/ml. If cycle length increase persists in these women for longer than 3 months, breast density in these women will be assessed first by breast MRI (because this involves no radiation exposure) and is likely to show changes. The pill supplement will be terminated in these women, but will be continued in the remaining study subjects. If cycle lengths increase in more than 30% of participants and this increase is study related, the pill intervention will be terminated and end of study mammography, bone density test by DEXA, and breast MRI will be performed.

If women develop amenorrhea, transvaginal probe ultrasonography and endometrial biopsies will be performed to ensure no adverse effects on the uterus. [name]. (a co-investigator) will prescribe and perform these tests. Study subject will be provided with a written pathological report for consultation with subject's own primary physician. Reports will also be provided to the Medical Monitor.

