During active data collection (e.g. screening, baseline and pill intervention periods), the data collection forms have subjects' names (to avoid making mistake), but these names will be wiped out from the forms and questionnaire and replaced with the assigned IDs as soon as the subjects complete the study. The PHQF is part of the subject's medical records and will be filed as such as soon as the subjects complete the study.

Each subject will be assigned a screening ID, BA001 to BA999 according to the

order they sign the informed consent which is also the order they enroll in the study. There may be dropouts during screening/baseline period but the ID of the dropouts once assigned will not be replaced. The subjects who complete the baseline study and if qualify to continue the pill intervention part of the study will be re-assigned another ID as PL001 to PL999 according to the order they begin the pill intervention portion of the study. Randomization will be made using PL IDs. The IDs are assigned by the Pharmacist and the key to the IDs is kept in the lock filing cabinets during active data collection. The Study Coordinators, PI, Dr. [name] (co-investigator physician responsible for subjects' well-being), and the Medical Monitor have access to this key during this period. After the completion of study, the key will be kept at the locked filing cabinet at the PI's office and at this stage, the PI, [name] and the Medical Monitor have access to the key.

Sample, image and record labeling: an example using subject PL001:

- Blood: PL001-S01 to PL001-S99 for sera, stored at -80°C
- Blood cells: PL001-C01 to PL001-C99, stored in liquid nitrogen tank
- Urine: PL001-U01 to PL001-U99, collected in a jug containing sodium azide and glycerol, stored at -20°C
- Nipple aspirate: PL001-N01(L,R) to PL001-N99(L,R); L, left breast; R, right breast, stored at -80°C
- Mammography: PL001-MM1La,b,c,d, or e (left breast, a to e views), PL001-MM1Ra,b,c,d, or e (right breast, a to e views)
- MRI: PL001-MR1L (left breast), PL001-MR1R (right breast)
- Bone density: PL001-D01-L2, L3, or L4 (lumbar spine 2, 3 or 4), PL001-D01-H (hip)
- Food Records: PL001-FR01 to PL001-FR99

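### The code-break rules do not say who learns the assignments, so the lead investigator and the density readers could be unblinded to 12 or more women while the trial continues

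*Combined protocol and SAP*

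**What the plan says.** Two separate safety rules lead to opened codes.

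- **Amenorrhea** (Experimental Design and Methods, pill supplementation period): "If more than 6% of subjects (12 subjects) develop amenorrhea, we will break the code for these women". The next step is "If amenorrhea is related to soy isoflavone treatment, the study will be terminated"; if the amenorrhea is judged unrelated, the trial goes on by implication. The plan adds that "a statistically significant change in breast density is then expected because the progesterone levels of these women will be <1 ng/ml".
- **Cycle lengthening** (Risk and Benefit Assessment): "If menstrual cycle lengths increase by more than 2 weeks in 12% of the participants (e.g. 12 subjects) for more than 3 cycles", then "the pill assignment codes for these women will be examined to assess if this is intervention-related". The sentence is passive and names no one. If the lengthening persists, "breast density in these women will be assessed first by breast MRI", with a change described as likely. Then: "The pill supplement will be terminated in these women, but will be continued in the remaining study subjects".

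On blinding, Experimental Design and Methods covers participants, research staff and investigators. The Mammography section says that the two threshold readers are blinded to pill assignment. It also says that the radiologist scoring BI-RADS sees images in random order without knowing assignment or dates. The MRI section has two team members jointly choose the segmentation thresholds and says nothing about masking them.

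On roles, Disposition of Data states "The IDs are assigned by the Pharmacist". It also mentions a Medical Monitor and gives the lead investigator, the coordinators and a physician co-investigator access to the ID key.

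**The concern.** Breast density is the primary outcome, and both the mammographic and the MRI measures depend on a threshold chosen by a person. The plan records in advance that it expects density to change in the very women whose codes would be opened. If the people choosing thresholds know those women's assignments, an expected direction and a judgement step coincide in the same images. At stake are possible bias in the primary comparison, and the credibility of the double-blind claim even if no bias occurs.

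The cycle-lengthening rule also produces an MRI outside the yearly schedule, only in women selected by an event after randomization. The analysis section does not say whether that scan counts as a post-baseline measure.

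**Working it through.** **1. The plan's own trigger counts.**
- Amenorrhea: 6% × 200 = 12, so the stated 12 reproduces. Read strictly, more than 6% begins at 13 (13/200 = 6.5%).
- Cycle lengthening: 12% × 200 = 24. The stated example of 12 fits only a base of 100 (12% × 100 = 12).

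The two rules therefore use different denominators, and the number of codes opened under the second could be 12 or 24.

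**2. Who could know, and who reads.**

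| Step | What the available text states |
|---|---|
| Amenorrhea code break | Done by the protocol's authors (first person plural) |
| Cycle-lengthening code check | Actor not named |
| Mammographic thresholds | Two trained team members, blinded to assignment; one appears, from the access list in Disposition of Data, to be the lead investigator |
| BI-RADS scoring | Radiologist; random order; unaware of assignment and dates |
| MRI thresholds | Two team members jointly; no masking stated in that section |
| Image labels | Carry the PL ID, which is also used for randomization |

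No entry separates those who open codes from those who set thresholds.

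**3. Illustrative effect on the arm difference.** Let k be the misread women in one arm, b the misreading per woman (assumed; the documents give no value) and n the number per arm. Shift = k × b / n. With k = 12, all on isoflavones, and n = 100:
- b = 5: 12 × 5 / 100 = 0.6 points
- b = 10: 12 × 10 / 100 = 1.2 points

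If only 6 of the 12 were on isoflavones and only those were misread, the shift would be 6 × 5 / 100 = 0.3 to 6 × 10 / 100 = 0.6 points.

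**4. Effect on type I error under the same assumption.** The standard error of the difference is SD × √(2/n): 2.83 for SD 20 and 1.41 for SD 10, the range in the power section. With λ = shift / SE, two-sided error = 1 − Φ(1.96 − λ) + Φ(−1.96 − λ).

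| Shift | SD 20 | SD 10 |
|---|---|---|
| 0.6 | 5.5% | 7.1% |
| 1.2 | 7.1% | 13.6% |

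**5. Deduction from block partners.** Randomization is in blocks of six, with three blood-draw subgroups per arm.
- If each block holds one woman per arm-by-subgroup cell (an assumption), each opened code also reveals the woman in the same block and subgroup. Simulating 33 full blocks, 12 codes reveal about 11.3 further women on average, or 12 if all are on isoflavones. The total is about 23 to 24.
- If blocks balance arm only, the further women revealed with certainty number about 0.03 to 0.14, effectively none.

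**The case against.** The strongest reply is that the plan already blinds investigators and threshold readers and gives the BI-RADS radiologist coded, randomly ordered images without dates. To shade a reading, someone would have to link an image to a particular woman and time point. That lowers the risk. It does not close the gap: random order and date masking are stated for the radiologist only, and a promise of blinding cannot by itself survive a code break by the same team.

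A reader might go further in several directions that the documents do not support.

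- **That codes will be broken.** Both rules are conditional on a trigger that may never fire.
- **That investigators open the codes and the trial then continues, under one rule.** This merges two rules. Only the amenorrhea rule uses the first person, and it ends the study if the amenorrhea is treatment-related. Twelve of 12 on isoflavones, the pattern behind the 0.6 to 1.2 points, is the one most likely to be judged related; with unrelated events its probability is about 0.0002 (0.5^12). Only the cycle-lengthening rule expressly continues, and it names no actor.
- **That the plan has no firewall.** Part of the roles section is not in the available text and may assign the codes. The claim is limited to what can be read.
- **That 24 women are exposed.** This needs arm-by-subgroup balance within blocks and readers able to reconstruct the blocks.
- **That a bias of 1.2 points has been shown.** The misreading is assumed. For scale, the difference detectable with 80% power at SD 20 and 100 per arm is (1.96 + 0.84) × 2.83, about 7.9 points.
- **That trigger-prompted MRI scans should be barred from the efficacy analysis.** The intent-to-treat set requires one post-baseline density measure. If a woman then left with that scan as her only one, barring it would remove her from the MRI analysis because of a suspected treatment effect.
- **That the ID key or the Pharmacist's role reveals treatment.** The text says that the Pharmacist assigns IDs and that the key identifies women. It does not say that either holds the treatment codes.

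**Conclusion.** The point holds in limited form. If either rule is followed as written, nothing in the available text stops the lead investigator or the density readers from learning the assignments of at least 12 women (13 on the strict reading of the amenorrhea rule, possibly 24 under the other) while the trial may still be running. That conflicts with the blinding promised elsewhere in the protocol.

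The size is illustrative and modest: 0.6 to 1.2 points if 12 isoflavone women are misread by 5 to 10 points, less if the opened codes are split between arms. Sample size and the power calculation are unaffected. The matter is worth fixing because the outcome depends on the reader, the expected direction is written down and the remedy is cheap.

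**What to change.** In both rules, state that existing roles outside density reading, such as the Medical Monitor with the Pharmacist, open the codes, compare counts by arm and report only a conclusion on relatedness. State that the lead investigator and all density readers stay blinded, and name the holder of the treatment codes. Extend the random-order and date masking already given to the BI-RADS radiologist to the mammographic threshold readings and the MRI readings. This matters because a relatedness conclusion, or stopping the supplement in certain women, is itself a hint about assignment.

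In Statistical Analysis, keep scheduled and exit scans in the primary model and state in advance how an unscheduled MRI is used. Add a sensitivity analysis without the women whose codes were opened. It should remain a sensitivity analysis, since it selects on an event after randomization.

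Reconcile the two rules' use of 12 subjects as 6% and as 12%. No threshold or clinical rule is proposed here.

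The cost is about a paragraph and no new staff if the named roles are used; the downside is slightly slower safety communication through the Medical Monitor. If the intervention is already complete, as the past tense in the post-intervention follow-up section suggests, report whether either trigger fired and who saw the codes, and run the sensitivity analysis.
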